### **6.8.2. Laboratory Data**

Knowledge of several clinical laboratory tests, including ALA, PBG, and ALAS1, has the potential to unblind the reviewer. Procedures to protect the blind, including permissions to view these lab values, are described in the Data Integrity Plan (Amendment 3, 07Sep2018).

Clinical laboratory values will be expressed in Standard International (SI) units. Missing laboratory data will not be imputed.

Summary data for each laboratory parameter will be presented for each continuous clinical laboratory parameter (including hematology, serum chemistry, liver function tests and coagulation studies). Descriptive statistics will be presented for the actual values, change from baseline, and percent change from baseline by visit.

Shift tables will be employed to summarize the baseline category versus the “worst” post-baseline category for selected parameters.

A listing will be produced for amylase and lipase in all patient with amylase/lipase observations above  $3\times\text{ULN}$  flagged. A listing for all patients with abnormal liver function tests defined as an  $\text{ALT} >3\times\text{ULN}$ ,  $\text{AST} >3\times\text{ULN}$ , or total bilirubin  $>2\times\text{ULN}$  at any time point will also be provided.

A table will be produced to summarize the number and percentage of patients in each of below category at any post-baseline time point.

- $\text{ALT} >1 \ \& \ \leq 3$ ,  $>3 \ \& \ \leq 5$ ,  $>5 \ \& \ \leq 10$ ,  $>10 \ \& \ \leq 20$ ,  $>20\times\text{ULN}$ ,
- $\text{AST} >1 \ \& \ \leq 3$ ,  $>3 \ \& \ \leq 5$ ,  $>5 \ \& \ \leq 10$ ,  $>10 \ \& \ \leq 20$ ,  $>20\times\text{ULN}$ ,
- $\text{ALT or AST} >1 \ \& \ \leq 3$ ,  $>3 \ \& \ \leq 5$ ,  $>5 \ \& \ \leq 10$ ,  $>10 \ \& \ \leq 20$ ,  $>20\times\text{ULN}$ ,
- $\text{ALP} > 1.5\times\text{ULN}$ ,
- Total Bilirubin  $>1.5 \ \& \ \leq 2$ ,  $>2 \ \& \ \leq 3$ ,  $>3 \ \& \ \leq 5$  and  $>5\times\text{ULN}$ ,
- Total Bilirubin  $> 1.5\times\text{ULN}$  concurrent with  $\text{ALT or AST} > 3\times\text{ULN}$ ,
- Total Bilirubin  $> 2\times\text{ULN}$  concurrent with  $\text{ALT or AST} > 3\times\text{ULN}$

EDISH plots for ALT, AST, and total bilirubin will also be provided.

For hematology and blood chemistry, summary tables of potentially clinically significant abnormalities will be provided. The results may also be graded according to the NCI CTCAE Version 4.0 or above. A shift summary of baseline to maximum post-baseline CTCAE grade may be presented, as appropriate.

All laboratory data will be provided in data listings. Out-of-range laboratory results will be identified in the listings.

### **6.8.3. Vital Signs and Physical Examination**

Descriptive statistics by visit and treatment arm will be provided for each variable.

Vital sign measurements will be presented for each patient in a data listing, with abnormal vital signs flagged.

### **6.8.4. Electrocardiogram**

Electrocardiogram (ECG) findings will include rhythm, ventricular rate, PR interval, QRS duration, QT interval, and QTc interval. For post-baseline assessments where ECG is performed in triplicate, the average of the 3 (or all available) readings will be used for analysis.

Corrected QT interval (QTc), if not collected, will be calculated using both Fridericia's and Bazett's correction formula.

Bazett's square-root corrected QT:  $QTcB \text{ (ms)} = QT \text{ (ms)} \times \sqrt{\frac{HR(bpm)}{60}}$

Fridericia's cube-root corrected QT:  $QTcF \text{ (ms)} = QT \text{ (ms)} \times \sqrt[3]{\frac{HR(bpm)}{60}}$ .

PR, QRS, QT, QTc (ie, QTcB and QTcF) and RR intervals and their change from pre-dose baseline will be summarized for each treatment group by scheduled visit. Subjects will be categorized into  $\leq 450$ ,  $> 450 - 480$ ,  $> 480 - 500$ , or  $> 500$  ms per their maximum post-baseline absolute QTc interval and  $\leq 30$ ,  $> 30 - 60$ , or  $> 60$  ms per their maximum change from baseline QTc interval. The number and percentage of subjects in each category will be summarized for each treatment group.

All ECG data for each patient will be provided in a data listing.

#### **6.8.5. Prior and Concomitant Medications**

Prior medications are those medications taken prior to the first dose of study drug. If the medication end date is before the date of first dose of study drug, the medication will be summarized as prior medication regardless of whether the start date is missing or not.

Concomitant medications are medications, other than study drug, taken at or after the first dose of study drug, as well as medications with a start date prior to first dose of study drug and are ongoing after first dose of study drug. If medication start date is on or after date of first dose of study drug, the medication will be summarized as concomitant medication regardless of whether the medication end date is missing or not. If the end date of a medication is missing or incomplete such that it cannot be determined whether it is before first study drug dose, it will be counted as a concomitant medication.

Prior and concomitant medications will be coded using the WHO Drug Dictionary (March 2018). Results will be tabulated by anatomical therapeutic class (ATC) and preferred term.

#### **6.9. Anti-Drug Antibody**

The number and percentage of patients with confirmed positive ADA assay results at any time during study as well as at each scheduled visit will be summarized. The titer results for patients with confirmed positive ADA results will also be summarized using descriptive statistics.

ADA data and patients with confirmed positive ADA results will be presented in data listings.

## 7. CHANGES FROM PREVIOUS VERSION(S)

### 7.1. Changes in SAP Amendment 1

The SAP Amendment 1 includes more details previously not discussed in the original SAP. Some changes to analysis methods are made following regulatory feedback and further assessments. Amendment 1 was signed off before the interim analysis. The details of changes and rationales are listed in below table.

Summary of Changes	Rationale
In the protocol and original SAP, an interim sample size reassessment (SSR) was planned but was not conducted during study.	An SSR was originally planned to be performed at the time of the interim analysis to potentially increase the number of AIP patients in the study from approximately 70 to 90. Due to fast enrollment of the study leading to greater than expected numbers of patients randomized, an interim analysis for SSR was therefore no longer necessary.
For the interim analysis of ALA at Month 3, the missing data imputation was mLOCF in the original SAP; in this amendment, the imputation will be based on MI. Additional sensitivity analyses are added including a PMM and a non-parametric method.	Updates made following regulatory feedback.
For the analysis of ALA/PBG at the end of 6m-DB period, the primary analysis was based on ANCOVA/mLOCF in the original SAP; in this amendment, the primary analysis for ALA/PBG will be based on MMRM and a sensitivity analysis using PMM is added for ALA.	Both MMRM and MI/ANCOVA are based on MAR assumption and MMRM is often considered a more simple and powerful method. PMM is added to assess the robustness of the results when missingness mechanism is MNAR.
For the analysis of primary endpoint attack rate, PMM is added to address potential missing attack data and other sensitivity analyses are added (Section 6.5.1.3).	These sensitivity analyses are added to assess the robustness of the primary analysis results.
The median instead of the mean of valid pre-dose values is used to derive baseline ALA/PBG.	Due to the variability with PD measures, the median is less affected by extreme values than the mean.
For the secondary endpoint PCS SF-12, the primary analysis method is changed from ANCOVA to MMRM.	This endpoint is measured at Month 3 and Month 6. MMRM implicitly imputes missing data using data from both time points while ANCOVA does not address missing data.
For the secondary endpoints daily worst score of pain, nausea, and fatigue, the AUC over 6 months will be derived by first calculating the weekly mean scores (Section 6.5.2).	Updated to address regulatory feedback on missing data handling and justification of AUC method.

## 7.2. Changes in SAP Amendment 2

In the SAP Amendment 2, detailed analyses for the entire study including OLE period are added. Amendment 2 will be signed off before the final analysis of the 6-month double-blind (6m-DB) data and the unblinding of treatment assignments.

In this version, a new analysis population All Givosiran Treated Set is added, additional subgroups of the All Givosiran Treated Set were defined to accommodate analysis of the different givosiran doses allowed in the OLE period with Protocol Amendment 3, and different treatment periods are defined to allow for the analysis of data in the overall study. In addition, Per Protocol Set is defined to allow for an evaluation of the primary endpoint in the subset of patients who fulfill the protocol in terms of the eligibility requirements, adherence to the study drug and outcome assessments. A few minor updates are made to the analysis of the 6m-DB period, e.g., zero-inflated negative binomial regression model is added to analyze components of attacks. For the analysis of worst scores of pain, fatigue, and nausea, the following updates are made:

- The AUC of weekly scores is updated as the AUC of change from baseline in weekly scores. Note that with an ANCOVA analysis adjusted for baseline, using the actual score or change from baseline as a response variable will yield the same estimate of treatment difference and p value. This update is made to allow for a direct estimate of the LS mean change from baseline in each treatment arm.
- The mean weekly score change from baseline over 6 months is defined for analysis, which is mathematically similar to the AUC of change from baseline in weekly score but is clinically meaningful and interpretable.
- The testing order of daily worst scores of fatigue and nausea are switched because the mean nausea scores at baseline are low therefore less likely to show improvement with treatment.

## 9. APPENDICES

### 9.1. Details of Interim Analysis

At the interim, the only efficacy endpoint to be assessed is the Month 3 ALA level in AIP patients. The other efficacy endpoints will not be analyzed. ALA data beyond 3 months will be summarized descriptively by treatment arm for each scheduled visit during the 6m-DB period. Patient disposition, demographic and baseline characteristics, drug exposure, safety, PK, and PD will be summarized as described in Section 6 .

#### 9.1.1. Interim Analysis Population

The analysis sets for the interim analysis are defined as follows:

- Interim Full Analysis Set (IFAS): a randomized patient will be included in the IFAS if
  - 1) the patient was randomized more than 92 days before the cutoff date; OR,
  - 2) the patient was randomized between 78 and 92 days before the cutoff date and both criteria below are met
    - a. the patient has finished the Month 3 visit on or before the cutoff date
    - b. all patients who have a randomization date before this patient are included

Patients will be grouped by their randomly assigned treatment group (i.e. as randomized) for the efficacy analyses.

- AIP patients in the Interim Full Analysis Set (IFASAIP)
- Interim Safety Analysis Set (ISAS): includes the same cohort of patients as in the IFAS but grouped according to the treatment actually received.

The primary efficacy analysis set for the ALA data is IFASAIP. The ALA data of the non-AIP patients who have finished the Month 3 visit in the IFAS will be presented in a listing. The safety analyses will be based on the ISAS and will also be performed for the AIP and non-AIP patients separately. PK analysis at interim will include patients who have evaluable PK data contributing to the estimation of PK parameters.

#### 9.1.2. Rationale for Month 3 ALA Endpoint

Three months of treatment is considered an appropriate time point for assessment of the efficacy of givosiran based on ALA levels observed in the givosiran Phase 1 study. In the Phase 1 study, there were 40 individual patients including 17 AIP patients with recurrent attacks, the patient population of the ENVISION study and 23 asymptomatic high excreters (ASHE, or chronic high excreters CHE). Among the 17 AIP patients with recurrent attacks, 3 patients were treated with givosiran at the Phase 3 dose (2.5mg/kg monthly) for three months and 4 patients were treated with placebo. The ALA levels for both treatment (N=3) and placebo (N=4) patients were plotted over time (in days) in [Figure 2](#) below. All three patients receiving givosiran experienced a rapid and robust decrease in ALA levels starting at Day 7 after the first dose, with plateau in ALA levels at Day 21 that was maintained throughout the entire dosing period (3 months).

**Figure 2: ALA Levels over Time (in Days) for Individual AIP Patients in the Givosiran Phase 1 Study (Cohort C)**

The planned sample size for the interim analysis is based on the following power considerations. Assuming the mean ALA levels (SD) at 3 months in the placebo and givosiran arms are 20.0 (11.1) and 2.3 (1.1) mmol/mol (based on Phase 1 study data), 40 AIP patients will yield more than 90% power in the ALA comparison at  $\alpha$  level of 0.001.

**9.1.3. Analysis of ALA Endpoint**

**9.1.3.1. Primary Analysis Using ANCOVA/Multiple Imputation**

The primary analysis to evaluate the treatment effect in ALA at Month 3 is an ANCOVA model, with multiple imputation (MI) assuming missing at random (MAR) in case of missing data at Month 3. The ANCOVA model includes baseline ALA as a continuous covariate and fixed effect terms including treatment arm and stratification factors for AIP patients (prior hemin prophylaxis status and historical attack rates). The significance level for the comparison at the interim is 0.001 (2-sided). Any ALA values measured within 3 days after hemin use will be excluded from the ALA analysis and will be treated as missing. The Least Square (LS) means, SEMs and 95% confidence intervals (CIs) for the LS means, difference in LS Means, and corresponding 95% CIs and p-value will be presented.

Missing data at Month 3 will be multiply imputed separately for each treatment arm using the Markov Chain Monte Carlo (MCMC) method following the MAR assumption. Treatment arm, the stratification factors, ALA measurements at baseline, Week 2, Month 1 and Month 2 will be included in the imputation model. One hundred imputed datasets will be generated using the SAS PROC MI procedure. Each of the imputed datasets will then be analyzed via the primary ANCOVA model. The LS means and standard errors will be combined using SAS PROC MIANALYZE to produce inferences including treatment difference in LS means, 95% CI for the treatment difference, and the p-value. Point estimates (LS means and treatment difference) will be calculated as the average of the 100 complete-data estimates. A total variance estimate will be calculated as a weighted sum of within-imputation variance, which is the average of the complete-

data variance estimates, and a between-imputation variance term. The sample code for performing the primary analysis is provide in Section 9.1.

### 9.1.3.2. Additional Analysis

When there is missing data at Month 3, the following sensitivity analyses will be conducted to assess the robustness of the primary analysis.

- Pattern mixture model (PMM) approach which accommodates situations where the missingness mechanism is missing not at random (MNAR). The details are described in Section 9.2 .
- Completer analysis: the primary ANCOVA model will be applied to analyze the subset of IFASAIP patients with non-missing Month 3 ALA value.

The upper limit normal (ULN) of the ALA level observed in the healthy volunteers is 1.5 mmol/mol Cr. The proportions of patients with Month 3 ALA levels below the thresholds of 1.5, 2, 3, and 4 times of the ULN in each treatment arm will be calculated. The difference between the proportions and the 95% exact confidence interval for the difference will be calculated. Patients with missing Month 3 ALA values will be included in the denominator.

Q-Q plot of the residual of the ANCOVA completer analysis will be provided for a visual examination of the normality assumption.

A non-parametric Wilcoxon rank sum test will be performed as a sensitivity analysis of the primary model.

### 9.1.3.3. Durability of ALA Lowering

The primary ANCOVA model (without missing data imputation) will be applied to evaluate the treatment effect at Week 2, Month 1 and Month 2. The LS mean ALA levels over time will be plotted for each treatment arm to assess the longitudinal treatment effect of Givosiran on ALA lowering. Spaghetti plots for individual patient will also be provided.

In the givosiran-treated arm, it is expected that there will be substantial ALA knockdown starting at Month 1 and maintained throughout the treatment duration. To assess the durability of treatment effect in ALA knockdown, the overall treatment effect over 3 post-baseline visits Month 1, Month 2 and Month 3 will be evaluated through a mixed effect model repeated measurement (MMRM). The MMRM model includes baseline ALA level as a continuous fixed covariate, stratification factors (prior hemin prophylaxis status and historical attack rates), visit and treatment as fixed factors, and patient as a random factor. An unstructured covariance matrix will be used to model the within-subject error. If the fit of the unstructured covariance structure fails to converge, a compound symmetry covariance structure will be used. The overall LS mean treatment difference measuring the average treatment effect on ALA from Month 1 to 3 and associated p value will be estimated.

## 9.2. Sample SAS Code for Interim Analysis of ALA Data

At the interim analysis, ANCOVA/MI is specified as the primary analysis of ALA data. The analysis is performed in 3 steps with sample SAS code provided below.

**Step 1.** 100 datasets will be imputed. Negative imputed values will be replaced by 0.10.

```
PROC MI data=&dsin. seed=1234 nimpute=100 out=&method._out;
    by treatment;
    em maxiter=300 converge=1e-4 itprint outem=outem;
    var &cov. &base. &varlist. &resp.;
    mcmc chain=multiple initial=em;
run;
*Apply truncations to negative imputed values;
data &method._out;
    set &method._out;
    if m3 < 0 then m3 = 0.10;
    if m2 < 0 then m2 = 0.10;
    if m1 < 0 then m1 = 0.10;
    if m0_5 < 0 then m0_5 = 0.10;
    if m0 < 0 then m0 = 0.10;
run;
```

Notes:

dsin=alydsv: an input dataset with treatment group, subject id, covariates (2 stratification factors in 0/1 format), creatinine normalized ALA at baseline (m0), week 2(m0\_5), Month 1 (m1), Month 2 (m2), and Month 3 (m3).

resp: m3

base: m0

trt: trt01p

cov: 2 stratification factors in 0/1 format

varlist: values at week 2, month 1 and 2 (m0\_5, m1, m2)

**Step 2.** The imputed datasets will be analyzed using ANCOVA model.

```
PROC MIXED data=&method._out method=reml;
    by _Imputation_;
    class &trt. (ref='Placebo') &cov.;
    model &resp.= &trt. &base. &cov. /ddfm=kr;
    lsmeans &trt. / pdiff=control('Placebo') cl diff;
    ods output lsmeans = &method._lsm;
    ods output diffs = &method._diff;
run;
```

**Step 3.** Combine the analysis results using Rubin's formula through PROC MIANALYZE.

```
PROC MIANALYZE data=&method._lsm;
    by &trt.;
    modeleffects estimate;
    stderr;
    ods output ParameterEstimates=&method._LSest;
run;
```

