## 5.7. Multiple Comparisons/Multiplicity

At the time of the unblinded interim analysis, only the first secondary efficacy endpoint ALA levels at Month 3 will be assessed. A significance level of 0.001 will be used when comparing the ALA levels between the two treatment arms using an ANCOVA model.

For the final analyses of the 6m-DB primary treatment period, a significance level of 0.049 will be used to test the efficacy endpoints, reflecting a penalty of 0.001 for the unblinded interim analysis. A fixed-sequence testing strategy for the primary and secondary endpoints will be implemented to control the overall type I error rate. The primary endpoint will be compared between treatment arms at the significance level of 0.049. If the test is statistically significant, then the secondary endpoints will each be tested at the same significance level of 0.049 in the order specified in the efficacy endpoint section (Section 3.2 ). If the test of an endpoint in the sequence is not statistically significant, the testing of remaining endpoints in the sequence will stop and the null hypotheses for the subsequent tests will not be rejected.

There will be no multiplicity adjustment for exploratory endpoints.

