The biomarker endpoints include the ALA levels in AIP patients ( $FAS_{AIP}$ ) at 3 months and 6 months, the urinary PBG levels in AIP patients ( $FAS_{AIP}$ ) at 6 months. Any postbaseline ALA/PBG values measured within 3 days after hemin use during the 6m-DB period will be treated as missing and excluded from analysis. For each biomarker secondary endpoint, the biomarker levels at the specified time point will be estimated and compared between two treatment arms using an MMRM model. The model will include baseline of the corresponding biomarker level as a continuous covariate, stratification factors (prior hemin prophylaxis status and historical attack rates), visit, treatment, and visit by treatment as fixed effects, and patient as a random effect. An unstructured covariance matrix will be used to model the within-subject error. If the fit of the unstructured covariance structure fails to converge, a compound symmetry covariance structure will be used. The least squares (LS) means and the corresponding SEM and 95% CIs for each treatment arm, along with the LS mean difference between two treatment arms at each post-baseline visit will be presented. The p-value for the treatment difference for each endpoint (ALA at Month 3 and Month 6; PBG at Month 6) will be presented. In addition, the overall p values measuring the average treatment effect on ALA and PBG during the entire 6m-DB period will also be reported to assess the durability of the treatment effect. If normal assumptions are violated, a non-parametric Wilcoxon rank sum test will be performed. For ALA at Month 3 and Month 6, if the drop-out rate during the 6m-DB period is  $\geq 5\%$  on the givosiran arm, sensitivity analyses will be performed using a PMM approach as described in Section 9.3.

Daily worst scores for pain measured by BPI-SF in Numeric Rating Scale (NRS), fatigue measured by BFI-SF in NRS, and nausea measured by NRS are collected through eDiary. For each of the symptoms (pain, fatigue and nausea), daily eDiary entries will be averaged into a weekly (i.e. 7 day) score. The change from baseline in weekly mean scores is defined as the post-baseline weekly mean score minus the baseline score. The AUC of change from baseline over 6 months in the respective measure will be calculated for each patient based on change from

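### The interim ALA model pools one residual variance over arms planned with SDs of 11.1 and 1.1, so the promised arm-level SEMs and 95% CIs are too narrow for placebo and too wide for givosiran

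*SAP*

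**What the plan says.** **Interim test.** SAP 5.7: "A significance level of 0.001 will be used when comparing the ALA levels between the two treatment arms using an ANCOVA model". SAP 9.1.3.1 lists the outputs, starting with "The Least Square (LS) means, SEMs and 95% confidence intervals (CIs) for the LS means", followed by the difference with its CI and p-value.

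**Interim code (SAP 9.2).** Step 1 imputes by treatment, matching SAP 9.1.3.1: "Missing data at Month 3 will be multiply imputed separately for each treatment arm". Step 2 is PROC MIXED with "model &resp.= &trt. &base. &cov. /ddfm=kr". It has no REPEATED statement and no GROUP= option, so both arms share one residual variance. Step 3 combines the arm-level LS means and standard errors in PROC MIANALYZE without giving complete-data degrees of freedom (EDF=).

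**Planning values (SAP 9.1.2).** "Assuming the mean ALA levels (SD) at 3 months in the placebo and givosiran arms are 20.0 (11.1) and 2.3 (1.1) mmol/mol". These are attributed to Phase 1, where "3 patients were treated with givosiran at the Phase 3 dose (2.5mg/kg monthly) for three months and 4 patients were treated with placebo".

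**Final ALA/PBG analysis (SAP 6.5.2).** "An unstructured covariance matrix will be used to model the within-subject error", with compound symmetry if that fails to converge. Outputs include "The least squares (LS) means and the corresponding SEM and 95% CIs for each treatment arm". No code is given and no grouping by arm is named. The interim durability MMRM (SAP 9.1.3.3) uses the same covariance wording.

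**The concern.** A single residual variance is an average of two arms whose planned SDs differ tenfold. Each arm's reported error is then built largely from the other arm's spread: placebo looks more precise than it is and givosiran less. The imputation step lets the variances differ and the analysis step that follows does not.

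What is at stake is mainly reporting. SAP 2.3 says the interim ALA result is for regulatory filing, and SAP 9.1.3.2 sets Month 3 ALA against multiples of an upper limit of normal of 1.5 mmol/mol Cr. An interval for the givosiran mean that runs below zero does not help to judge how near to normal these patients come. A second question is whether the 0.001 test keeps its level.

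**Working it through.** **Inputs.** Means 20.0 and 2.3, SDs 11.1 and 1.1, 40 AIP patients, alpha 0.001 two-sided (SAP 9.1.2, 9.1.3.1); 1:1 allocation (SAP 2.2), taken as 20 per arm; final alpha 0.049 (SAP 5.7). Baseline correlations, the between-visit correlation and the baseline distribution are assumptions, because the documents give none.

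**The plan's own figure.** Pooled SD = sqrt((11.1² + 1.1²)/2) = 7.89. SE of the difference = 7.89 × sqrt(2/20) = 2.49. Planned t = 17.7/2.49 = 7.1. Power at 0.001 is 99.9% with 38 df and 99.7% with the Welch df of 19.4. The stated power of more than 90% is reproduced either way.

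**Arm level, no covariate, 20 per arm**

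| | Pooled model | Own variance |
|---|---|---|
| Placebo SEM | 7.89/√20 = 1.76 | 11.1/√20 = 2.48 |
| Givosiran SEM | 1.76 | 1.1/√20 = 0.246 |
| 95% half-width, placebo | 3.57 | 5.19 |
| 95% half-width, givosiran | 3.57 | 0.51 |

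The placebo SEM is 1.76/2.48 = 0.71 of its true value, and its nominal 95% CI covers 83%. The givosiran SEM is 1.76/0.246 = 7.2 times too large. At the planned mean, the givosiran CI is 2.3 ± 3.57 = -1.3 to 5.9, against 1.8 to 2.8 with its own variance.

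**With baseline ALA and two strata, 20 per arm (simulation).** Assumed baseline correlation is 0.5 or 0.8 on placebo and 0.3 on givosiran. Placebo noise reaches the givosiran LS mean through the shared slope and strata terms, so the givosiran excess shrinks.

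| Data, placebo correlation | Placebo coverage | Givosiran SE ratio | Givosiran lower limit below 0 |
|---|---|---|---|
| Normal, 0.5 | 85.4% | 2.09 | 89.1% |
| Normal, 0.8 | 88.8% | 1.35 | 72.6% |
| Lognormal, 0.5 | 83.3% | 2.02 | 78.2% |
| Lognormal, 0.8 | 86.0% | 1.30 | 60.9% |

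By-arm variances give coverage of about 93-95%. A separate run with the same correlation in both arms (0.5, 0.8) gave a mean model SEM of 1.66 and 1.41. The actual values were 2.40 and 2.18 for placebo and 0.64 and 0.77 for givosiran (ratios 2.6 and 1.8). The direction is the same; the size depends on the assumptions.

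**Final MMRM, one covariance matrix for both arms** (seven visits, 35 per arm, between-visit correlation 0.75 assumed, ALA at Month 3): placebo coverage 83-88%, givosiran SE 1.6-2.8 times too large, lower limit below zero in 36-62% of trials.

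**Uncertainty in the SD ratio.** 11.1/1.1 = 10.1. If the SDs come from 4 and 3 patients, the F interval (3 and 2 df, normality assumed) is 1.6 to 40. Without covariates, a ratio of 1.6 gives placebo coverage of 90% and a givosiran SE 1.3 times too large; a ratio of 3 gives 86% and 2.2 times.

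**Interim test size at 0.001, equal means, no covariate, t reference**

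| Placebo/givosiran | SDs | One variance | By arm (Welch) |
|---|---|---|---|
| 20/20 | 11.1, 1.1 | 0.0020 | 0.0010 |
| 18/22 | 11.1, 1.1 | 0.0048 | 0.0010 |
| 22/18 | 11.1, 1.1 | 0.0007 | 0.0010 |
| 20/20 | equal | 0.0010 | 0.0009 |

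At 20/20 the SE of the difference is 2.49 either way; only the df differ (38 against 19.4). If Step 3 uses a near-normal reference because EDF= is absent and little is missing, the size at 20/20 is about 0.004 with or without by-arm variances.

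**The case against.** A reader might infer that the interim test fails to hold its level and that type I error control is compromised. The documents do not support that. The inflation needs equal means together with a tenfold SD gap. The planning CVs are 11.1/20.0 = 0.56 and 1.1/2.3 = 0.48, so the SD gap comes largely with the mean effect. If givosiran did nothing to ALA, the arms would share one variance and the size would be 0.001. The direction also reverses when placebo has more patients. At the final analysis, an unadjusted two-sample test gives 0.053 against 0.049. The simulated MMRM with common covariance, which is closer to the plan, gives 0.045 at 35/35 (Monte Carlo SE about 0.005). Its 0.070 at 30/35 rests on an assumed imbalance. Protocol 4.1 and 6.3.1 move urine sampling to at least 4 days after hemin, so loss under the SAP's 3-day exclusion should be limited.

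Other fair points: the factor of 7 ignores the planned covariates; the MMRM part rests on what SAP 6.5.2 leaves unsaid; and SAP 9.1.3.3 promises no arm-level SEMs. Unpooled descriptive statistics by arm and visit (SAP 5.2, 6.6), individual plots (9.1.3.3) and threshold proportions (9.1.3.2) will show the true spread.

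These points make the test-size effect conditional and reduce the headline factor. They leave the arm-level intervals uncorrected. The Q-Q plot and Wilcoxon tests address normality, the pattern mixture model addresses missing data, and descriptive SDs do not change model-based SEMs and CIs that the SAP commits to report.

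**Conclusion.** The concern holds for the arm-level intervals. As coded, the interim ANCOVA will report placebo SEMs and CIs that are too narrow (coverage about 83-89%). Those for givosiran will be too wide, by about 1.3-2.1 times with the baseline covariate under the main assumed correlations and about 7 times without it. The final ALA/PBG MMRM would share the defect if fitted with the usual single covariance matrix; its size for PBG cannot be stated. All sizes rest on planning SDs that apparently come from 4 and 3 Phase 1 patients and on assumed correlations.

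The effect on the 0.001 test is secondary and conditional: about 0.002 at 20/20 with equal means, these SDs and a t reference, and 0.001 with equal variances. With a planned t of about 7 and by-arm power of 99.7%, the conclusion at the planned effect does not change. The change should be made because the reported error bars are wrong as written and the interim correction is cheap.

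**What to change.** - **SAP 9.1.3 and 9.2.** Let the residual variance differ by arm (REPEATED / GROUP=treatment, keeping ddfm=kr), in line with the by-arm imputation. Pass the resulting degrees of freedom to PROC MIANALYZE through EDF= for each arm mean and for the difference, since GROUP= alone does not correct the test size.
- **SAP 6.5.2.** State that arm-level SEMs and CIs come from a model with arm-specific covariance and Kenward-Roger or Satterthwaite df, with a by-arm structured covariance as the convergence fallback. Keep the planned common-covariance MMRM for the test, and say so. In SAP 9.1.3.3, state whether the covariance differs by arm.
- **Sensitivity analysis.** Prespecify log(ALA) and log(PBG) with log baseline, reporting geometric means and their ratio. With log SD = sqrt(ln(1 + CV²)), the planning values for ALA are nearly equal on that scale (0.52 and 0.45).

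**Cost.** SAP wording, one model option, one sensitivity analysis and slightly more analysis work. For seven visits, a by-arm unstructured matrix has 56 parameters against 7 × 8/2 = 28, with some convergence risk at about 35 per arm. The interim difference loses some precision: SD of the estimate 2.47 against 2.43 at assumed placebo correlation 0.5, and 2.42 against 2.13 at 0.8. Using the by-arm MMRM for the test would cost more (1.83 against 1.77, and 1.80 against 1.54), which is why it is confined to arm-level reporting.
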